### 6.3 Reporting to the Ethics Committee

The sponsor will assess whether any relevant safety information that becomes available during the study should be reported ad hoc to the EC.

The sponsor has the obligation to, once a year throughout the clinical trial (or on request), submit a progress report to the EC containing an overview of all SARs occurred during the reporting period and taking into account all new available safety information received during the reporting period.

## 7. Ethics and regulatory approvals

### 7.1 Regulation statement

The study will be conducted in compliance with the principles of the Declaration of Helsinki (Fortaleza, Brazil, October 2013) and in accordance with the Medical Research Involving Human Subjects Act (WMO) and other guidelines, regulations and Acts.

The study protocol and all other study-related information shall be submitted to the Ethics Committees of the Participating Sites and the national competent authorities where applicable, in order to obtain prior approval before the study is initiated, unless such submission to the Ethics Committee is not required by applicable national legislation or in the event of a waiver for submission has been granted. Any subsequent protocol amendments will be submitted to the appropriate Ethics Committees and national Regulatory Authorities for approval.

Unless not required by applicable national legislation, the study will be conducted only on the basis of prior informed consent by the study subjects, or their legal representatives, to participate in the study. The Participating Site shall

obtain a signed informed consent form (ICF) for all patients prior to their enrolment and participation in the study in compliance with all applicable laws, regulations and the approval of the (local) Ethics Committee, if required. The Participating Site shall retain such ICFs in accordance with the requirements of all applicable regulatory agencies and laws.

The Investigator and the Participating Site shall treat all information and data relating to the study disclosed to Participating Site and/or Investigator in this study as confidential and with respect for the study participant's privacy and shall not disclose such information to any third parties or use such information for any purpose other than the performance of the study. The collection, processing and disclosure of personal data, such as patient health and medical information is subject to compliance with applicable personal data protection and the processing of personal data (EU Directive 95/46/EC and its transposing national legislation).

The data shall be coded, which means that there continues to be a link between the data and the individual who provided it. The research team is obligated to protect the data from disclosure outside the research team according to the terms of the research protocol and the informed consent document. The subject's name or other identifiers should be stored separately from their research data and replaced with a unique code to create a new identity for the subject. Note that coded data are not anonymous.

### **7.2 Recruitment and consent**

Couples will be asked for informed consent on the day of their oocyte aspiration. Patients who agree to participate will be asked to sign a written informed consent of which they will receive a copy.

### **7.3 Compensation for injury**

The sponsor has obtained dispensation from the statutory obligation to provide insurance. Due to the nature of the study, there are no additional risks.

### **8. Publication policy**

The parties agree that publications or presentations of any of the results from the study shall be in accordance with accepted scientific practice, academic standards and customs. It is anticipated that the results of the overall study shall be published in an international peer reviewed journal. Publications will be coordinated by [name]. Authorship to publications will be determined in accordance with the requirements published by the International Committee of Medical Journal Editors and in accordance with the requirements of the respective medical journal.

### **9. Insurance/indemnity**

Sponsor shall be liable, even without fault, for any damages incurred by a study patient and linked directly or indirectly to the participation to the study. Sponsor shall enter into an insurance agreement in order to cover the liability for any damages incurred by the Belgian study participants.

### **10. Funding**

Not applicable.

## 12. Appendices

### Appendix 1: Questionnaire on IVF-live birth rates expected by patients

[figure not shown]
[figure not shown]
---

Your gynaecologist told you which success rates he/she expects in your case but we are interested in your expected IVF-live birth rate.

**What, do you think, is the chance that you or your partner will deliver after all the embryo transfers of your current IVF/ICSI-cycle?**

This includes both the current fresh embryo transfer and, in case embryos have been frozen, subsequent frozen embryo transfers.

(Please indicate your response with a 'X' on the bar below, the arrows below explain the meaning of some possible answers)

## Appendix 2: LOT-R questionnaire on general optimism (Scheier et al, 1994)

---

Please be as honest and accurate as you can throughout. Try not to let your response to one statement influence your responses to other statements. There are no "correct" or "incorrect" answers. Answer according to your own feelings, rather than how you think "most people" would answer.

In uncertain times, I usually expect the best.

- I agree a lot
- I agree a little
- I neither agree nor disagree
- I disagree a little
- I disagree a lot

It's important for me to keep busy.

- I agree a lot
- I agree a little
- I neither agree nor disagree
- I disagree a little
- I disagree a lot

It's easy for me to relax.

- I agree a lot
- I agree a little
- I neither agree nor disagree
- I disagree a little
- I disagree a lot

I hardly ever expect things to go my way.

- I agree a lot
- I agree a little
- I neither agree nor disagree
- I disagree a little
- I disagree a lot

If something can go wrong for me, it will.

- I agree a lot
- I agree a little
- I neither agree nor disagree
- I disagree a little
- I disagree a lot

I don't get upset too easily.

- I agree a lot
- I agree a little
- I neither agree nor disagree
- I disagree a little
- I disagree a lot

I'm always optimistic about my future.

- I agree a lot
- I agree a little
- I neither agree nor disagree
- I disagree a little
- I disagree a lot

I rarely count on good things happening to me.

- I agree a lot
- I agree a little
- I neither agree nor disagree
- I disagree a little
- I disagree a lot

I enjoy my friends a lot.

- I agree a lot
- I agree a little
- I neither agree nor disagree
- I disagree a little
- I disagree a lot

Overall, I expect more good things to happen to me than bad.

- I agree a lot
- I agree a little
- I neither agree nor disagree
- I disagree a little
- I disagree a lot

### Appendix 3: the STAI-state questionnaire on state anxiety

---

A number of statements which people have used to describe themselves are given below. Read each statement and then circle the appropriate number to the right of the statement to indicate how you feel right now, that is, at this moment. There are no right or wrong answers. Do not spend too much time on any one statement but give the answer which seems to describe your present feelings best.

	Not at all	Somewhat	Moderately so	Very much so
I feel calm				
I feel secure				
I am tense				
I feel strained				
I feel at ease				
I feel upset				
am presently worrying over possible misfortunes				
I feel satisfied				
I feel frightened				
I feel comfortable				
I feel self-confident				
I feel nervous				
I am jittery				
I feel indecisive				
I am relaxed				
I feel content				
I am worried				
I feel confused				
I feel steady				
I feel pleasant				

**Appendix 4: IDS questionnaire on infertility specific distress (Pook&Krause, 2005)**

---

This questionnaire deals with your distress due to your (couple) infertility. Please indicate what applies best to you at this moment in time.

		Not at all	A little	Somewhat	A lot	Very much
1	To which extend are you distressed due to the last menstruation (and therefore no pregnancy)?					
2	To which extend are you distressed due to your infertility as a whole?					
3	To which extend is having a child important to you?					
4	To which extend do you appraise your infertility as a challenge?					
5	To which extend do you appraise your infertility as a threat?					
6	To which extend do you feel helpless due to your infertility?					
7	How often do you think of your infertility?					
8	How big is your desire to have a child?					

**Appendix 5: Document with personalized information given at the time of embryo transfer to patients in the intervention group**

NAAM PATIENT NAAM PARTNER GAP-CS-XX	811111V111 811111M111	
<h2>GYNAECOLOGIST'S FEEDBACK ON ART-PREGNANCY RATES</h2>		
Jouw embryo ('s)		
		
Kwaliteit		
Het aantal ingevroren embryo's van deze cyclus:		3
Gepersonaliseerde zwangerschapskans voor deze cyclus (= verse embryotransfer + transfer van ingevroren embryo)		38.39%

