## 0. Study synopsis

Study title	Gynecologists' feedback on ART-Pregnancy rates: a Randomized Controlled Trial
Short title	GAP-RCT
Sponsor name	KU Leuven
Principal Investigator	[name]. [name] (UZ Leuven)
Medical condition/ disease under investigation	Infertility treated with IVF
Study purpose	
We will examine the hypothesis that women who are given their personalized IVF-prognosis are less likely to overestimate their IVF-live birth rate, as compared to women who do not receive a personalized IVF-prognosis.
 
Control group: At the time of their fresh embryo transfer couples will receive a document with a photo of their transferred embryo(s) and the number of cryopreserved embryos.
 
Intervention group: At the time of their fresh embryo transfer couples will receive a document with the following feedback: a photo of their transferred embryo, the number of cryopreserved embryos, the quality rating of the transferred embryo's (i.e. ★, ★★, ★★★, ★★★★), and couple's personalized IVF-prognosis (i.e. their chance on a live birth from the current IVF-cycle, including the transfer of fresh and if available cryopreserved embryos, calculated by entering eight background characteristics and five IVF-laboratory results into a prognostic model).

Primary outcome	The proportion of women expecting their IVF-live birth rate to be double their calculated IVF-prognosis , directly after their fresh embryo transfer.
Secondary outcomes	
The proportion of men expecting their IVF-live birth rate to be double their calculated IVF-prognosis, directly after their fresh embryo transfer.
 
Women's and men's anxiety will be assessed with the reliable 'State-Anxiety Inventory, (STAI-state)' questionnaire, disseminated in coded paper-pencil format on the day of the fresh embryo transfer.
 
Patient's infertility-specific distress will be assessed with the reliable 'Infertility Distress Scale (IDS)' questionnaire, disseminated via text message and online within two days of the conclusive pregnancy test after the transfer of the last (fresh or cryopreserved) embryo of the studied IVF-cycle.

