## 2. Study objectives and design

### 2.1 Study objective

We will examine the hypothesis that women who are given their personalized IVF-prognosis are less likely to overestimate their IVF-live birth rate, as compared to women who do not receive a personalized IVF-prognosis.

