### 2.2 Study design

At the time of oocyte aspiration, patients will be randomised in two groups:

- Control group: At the time of their fresh embryo transfer couples will receive a document with a photo of their transferred embryo(s) and the number of cryopreserved embryos.
- Intervention group: At the time of their fresh embryo transfer couples will receive a document with the following feedback (Appendix 5): a photo of their transferred embryo, the number of cryopreserved embryos, the quality rating of the transferred embryo's (i.e. ★, ★★, ★★★, ★★★★, appendix 6), and couple's personalized IVF-prognosis (i.e. their chance on a live birth from the current IVF-cycle, including the transfer of fresh and if available cryopreserved embryos), calculated by entering eight background characteristics and five IVF-laboratory results into a prognostic model (Appendix 7).

Firstly, we wish to analyse whether personalized information on IVF-prognosis on the day of their fresh embryo transfer results in more realistic expected IVF-live birth rates.

Secondly, we wish to evaluate whether sharing these IVF-prognosis with patients at the time of embryo transfer is associated with the anxiety experienced by patients.

Thirdly, we wish to explore whether these IVF-live birth rates expected by patients are associated with the infertility specific distress experienced by patients at the time of a negative pregnancy test.

Fourthly, we wish to follow-up whether these IVF-live birth rates expected by patients are associated with clinical and compliance outcomes.

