### 2.3 Study parameters/endpoints

The **primary endpoint** is the proportion of women expecting directly after their fresh embryo transfer that their IVF-live delivery birth rate to be double their calculated IVF-prognosis (i.e. women's expected live birth rate  $\geq 2^* \text{prognose}$ ) In addition the proportion of men expecting their IVF-live birth rate to be double their calculated IVF-prognosis will be studied. Patient's expected IVF-live birth rates will be assessed immediately after the fresh embryo transfer with a single question coded paper-pencil questionnaire.

**Women's and men's anxiety** will be assessed with the reliable 'State-Anxiety Inventory, (STAI-state)' questionnaire disseminated in coded paper-pencil format on the day of the fresh embryo transfer (Appendix 3). The STAI-state questionnaire includes 20 questions rated on a-four-point-Likert scale and results in a score between 20 to 80 (the higher, the more anxiety).

**Patient's infertility-specific distress** will be assessed with the reliable 'Infertility Distress Scale (IDS)' questionnaire, which has been translated reciprocally to Dutch (Appendix 4). The IDS questionnaire will be disseminated via text message and online within two days of the conclusive pregnancy test after the transfers of the last (fresh or cryopreserved) embryo of the studied IVF-cycle. The IDS questionnaire includes eight questions to be rated on a-five-point-Likert scale and results in a score between 8 and 40 (the higher, the more infertility specific distress, Appendix 4).

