### 3.2 Study procedures including recruitment and data-collection

The main outcomes of this study are gathered on the days of OPU and Embryo transfer as presented in figure 1.

[figure not shown]

Figure 1: Study procedure and data collection for participating couples of the GAP-RCT

**On the day of their oocyte aspiration**, couples will be informed on the study and asked for their informed consent. Consenting men and women of eligible couples will be asked to each fill out a questionnaire on expected live birth rate (Appendix 1) and the LOT-R questionnaire (Appendix 2) on general optimism.

**On the day of their fresh embryo transfer**, couples are randomized. Couples in the control group receive a document with a photo of their embryo(s) and the number of cryopreserved embryos. Couples in the intervention group receive a document with a photo of their transferred embryo(s), its quality rating, the number of cryopreserved embryos and couple's personalized IVF-prognosis (Appendix 5). Men and women of both groups will be asked to fill out the questionnaire on expected live birthrate (Appendix 1) and the STAI-state questionnaire on anxiety (Appendix 3).

**Within two days of the conclusive pregnancy test** after the transfers of the last (fresh or cryopreserved) embryo of the studied IVF-cycle, the IDS questionnaire on Patient's infertility-specific distress will be disseminated via text message and online (appendix 4).

**Eighteen months after the embryo transfer** of the last (fresh or cryopreserved) embryo of the studied IVF-cycle, the researchers will follow-up the long-term clinical and compliance outcomes in patient's medical chart (i.e. censored by their medical doctor to discontinue IVF, IVF-delay and IVF-discontinuation).

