### 4.3 Quantification of the under/over estimation of the live birth rates expected by patients

In addition to the primary outcome (i.e. evaluating the proportion of women expecting their IVF-live birth rate to be double their calculated IVF-prognosis directly after their fresh embryo transfer) we want to quantify this under/over estimation. This will be calculated using the following formula: (expected LBR-prognosis)/prognosis. A positive sign shows overestimation, a negative sign shows underestimation and the absolute value quantifies the extend of the over/underestimation. For both groups, the mean and SD will be calculated. In addition, the mean difference in misjudgement between both groups and its 95% confidence interval (i.e. to give an impression of the preciseness of this estimation) will be reported.

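### The intervention sheet in Appendix 5 labels the prognosis a pregnancy chance, although the protocol defines the same number as a live-birth chance and scores it against expected live birth or delivery.

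*Combined protocol and SAP*

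**What the plan says.** Appendix 5 is titled "Document with personalized information given at the time of embryo transfer to patients in the intervention group". The line above its example value of 38.39% reads "Gepersonaliseerde zwangerschapskans voor deze cyclus (= verse embryotransfer + transfer van ingevroren embryo". *Zwangerschapskans* is Dutch for chance of pregnancy. The sheet's heading also speaks of pregnancy rates, and nothing in the template text mentions live birth or delivery.

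Elsewhere the same number is a live-birth chance. The synopsis defines the prognosis as the chance of a "live birth from the current IVF-cycle, including the transfer of fresh and if available cryopreserved embryos, calculated by entering" background and laboratory data into the model. Section 2.2 repeats the definition ("their chance on a live birth from the current IVF-cycle") and points to Appendix 7 for the calculation. Appendix 8, the uptake questionnaire, tells patients that the sheet gave them a chance of live birth.

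The measures also concern live birth. The hypothesis in section 2.1 is that "women who are given their personalized IVF-prognosis are less likely to overestimate their IVF-live birth rate". The primary endpoint in section 2.3 is the "proportion of women expecting directly after their fresh embryo transfer that their IVF-live delivery birth rate to be double their calculated IVF-prognosis". The misjudgement measure in section 4.3 takes the expected live birth rate minus the prognosis, divided by the prognosis. Appendix 1 asks how likely a delivery is once all fresh and frozen transfers of the cycle are done.

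For controls, section 3.2 says: "Couples in the control group receive a document with a photo of their embryo(s) and the number of cryopreserved embryos". Their sheet carries no prognosis.

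**The concern.** The sheet is the intervention. Women read it and are asked, directly after transfer, for their expected chance of delivery; that answer is scored against the number on the sheet. A woman who takes the label literally can reason that some pregnancies end in loss and answer below the printed figure. She would be recorded as underestimating although she believed what she was told.

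Only the intervention sheet carries the label, so this particular misreading can arise in one arm only. It pushes in one direction, towards lower stated expectations. Feedback would then look better at lowering expectations than a correctly labelled number would. The section 4.3 ratio is the more exposed measure, because it moves with any shift in the answer. The primary endpoint moves only if an answer crosses twice the prognosis.

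**Working it through.** **Is it the same number?** Section 3.2 says that intervention couples receive the personalised prognosis and refers to Appendix 5 for it. Section 2.2 defines that prognosis as a live-birth chance over fresh plus frozen transfers. The Appendix 5 line has the same fresh-plus-frozen scope. The scope agrees and the named event does not. Nothing in the documents says that *zwangerschapskans* is meant as live birth.

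**Can the model settle it?** Appendix 7 lists coefficients and a formula for the prognosis but does not name the predicted outcome. The label cannot be checked there.

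**Inputs for the illustration**
- P = 38.39%, the example in Appendix 5.
- Threshold for the primary endpoint: 2 x 38.39 = 76.78% (rule in section 2.3).
- d = proportion of pregnancies not ending in live birth. It is not in the documents; assumed 0.10 to 0.25.
- r = the answer a woman would give without discounting, divided by P.
- s = share of intervention women who discount. Unknown.

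**A woman who accepts the number (r = 1)**
- d = 0.10: 38.39 x 0.90 = 34.55%, which is 3.84 points below her prognosis.
- d = 0.25: 38.39 x 0.75 = 28.79%, which is 9.60 points below.
- Section 4.3 ratio: (P(1-d) - P)/P = -d, so -0.10 to -0.25 instead of 0.

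**Any other woman**
- Without discounting, her ratio is r - 1. With it, the ratio is r(1-d) - 1. The shift is -d x r.
- At r = 2, for example, the shift is -0.20 to -0.50.

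**Group mean of the section 4.3 ratio**
- If a share s discounts, the mean moves by -d x s x (mean r among those women).
- With r = 1 for all of them: s = 0.25 gives -0.025 to -0.0625; s = 0.50 gives -0.05 to -0.125; s = 1 gives -0.10 to -0.25.
- These group figures are illustrative only. Section 3.1.2 assumes that 25% of women still expect at least double their prognosis after feedback, so r = 1 does not describe the whole group.

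**Primary endpoint**
- A woman changes category only if r is at least 2 and r(1-d) is below 2, that is, 2 <= r < 2/(1-d).
- d = 0.10: 2/0.90 = 2.22. d = 0.25: 2/0.75 = 2.67.
- An answer cannot exceed 100%, so in the 38.39% example r stops at 100/38.39 = 2.60.
- The documents give no distribution of r, so the number of such women cannot be derived.

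**Sample size.** The planned 64 per group for 50% against 25% (two-sided, alpha 0.05) reproduces with Fisher's exact test: power is 79.4% at 63 and 80.2% at 64. The label does not enter this calculation.

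**The case against.** Several points on the other side stand.

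- **Controls may have heard a figure.** Appendix 1 goes to both groups and opens by telling respondents that their gynaecologist has already told them the success rates expected in their case. Controls may therefore have been given a rate orally, in wording that is not shown. A reader might infer that controls cannot be affected by pregnancy-versus-birth wording at all. The documents support only that the control sheet carries no number.
- **Other material may clarify.** Appendix 1 says that it concerns the expected live birth rate. Appendix 8 calls the printed number a live-birth chance, and the synopsis places its questions on the day of transfer, but the order relative to Appendix 1 is not stated. This may soften a misreading and does not exclude one.
- **Pregnancy is used loosely.** The trial title itself speaks of pregnancy rates while the objective is live birth. Dutch patients may take *zwangerschapskans* as the chance of a child. Only an English Appendix 1 is shown, so the agreement of the two Dutch forms cannot be checked.
- **The effect is hypothetical.** The loss rate is assumed, and nothing in the documents shows that patients discount. The section 4.3 measure is a descriptive estimate with a confidence interval and no stated test.

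These points limit the size of the effect. They do not remove the contradiction between the sheet and the definition.

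A reader might also infer that the model really predicts pregnancy, since the title of the development study cited for it (reference 8) refers to chances of pregnancy. The prognosis would then be too high in both arms, and with the same assumed 10% to 25% loss the example threshold would be 69.1% to 57.6% instead of 76.78%. The documents do not support this. A title does not show what the adapted model was fitted to, and section 2.2 ties the live-birth definition to Appendix 7 in one sentence. The silence of Appendix 7 on its outcome is a reason to check and no more.

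**Conclusion.** The point holds as a labelling error in the document that delivers the intervention. That the label contradicts the protocol's own definition follows from the text and needs no assumption.

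The consequence is less certain. A woman who believes the sheet and discounts for loss would score -d x r lower on the section 4.3 ratio. That is 0.10 to 0.25 lower when she otherwise accepts the number, if the loss rate is 10% to 25%. The share of women who would do so is unknown and may be small. The effect on the primary endpoint is probably small, because it needs a woman who discounts the printed number and whose undiscounted answer would still have been at or modestly above twice that number. It would be going too far to conclude that the primary comparison is biased to a known degree or is invalid. The sample size and power are unaffected.

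The label should still be corrected. The possible distortion favours the intervention, comes from one arm's document, and is cheap to remove.

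**What to change.** First confirm from the model fit that the outcome in Appendix 7 is live birth, and preferably say so there in one sentence. Then relabel the Appendix 5 line as the chance of a live birth from this cycle, fresh plus frozen transfers, so that it matches section 2.2, Appendix 1 and Appendix 8. Check the Dutch Appendix 1 for the same wording.

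The cost is one label, one check of the model fit, and an amendment. Section 7.1 requires amendments to go to the ethics committees and national regulatory authorities for approval, so notification alone would not be enough. No extra patients or data are needed.

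If the check shows that the model was fitted to pregnancy, relabelling is not enough. The prognosis would need correction before it is used in the endpoint, which should stay on live birth as in section 2.1. That work is not included in the cost above.
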